**Significance of this study (why is it important, what new information will it provide?)**

Currently the recommended treatment for septic arthritis is surgical irrigation and debridement in an urgent manner (<24 hours from presentation). However, with the increasing utilization of arthroscopic approaches to orthopedic cases, there has not been an established optimal surgical approach to intra articular knee irrigation and debridement. Surgeons most often rely on their own preference (i.e. arthroscopic versus open approaches), however there has not been an established optimal surgical approach. Ultimately all patients undergo operative management (and repeated trips to the operating room, if needed). However, newer retrospective studies have shown clinical benefit with

shorter hospital stays, lower number of repeated trips to the operating room, and overall improved patient satisfaction when treated with arthroscopic surgical management of septic arthritis of the knee.

This study would help solidify in a randomized control trial the most appropriate surgical approach to septic arthritis of the adult native knee.

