## **Study Design & Methods (include the following information):**

### **Human Study Subjects:**

#### *A.) Informed consent process and timing of obtaining consent*

Study recruitment will take place in the emergency department. All adult patients (>18 years) who have a clinically established diagnosis of septic arthritis in the emergency department based on the following will be considered for study inclusion and approached for offering participation in our study:

- Arthrocentesis with synovial WBC > 50,000 with left shift (85% PMNs)
- AcrySTALLINE (without gout crystals) elevated synovial WBC >25,000  
with high clinical suspicion
- Willingness to participate in this research study

Once the arthrocentesis results have confirmed the above inclusion criteria, the orthopedic resident who is managing the patient's care will contact one of the study investigators. In the meantime, the orthopedic resident managing the patient's care will obtain consent for surgery and book the patient for the operating room to ensure there is not a delay in patient care.

One of the study investigators will perform a face to face introduction of the study to the patient in the emergency department prior to the operative management. Their diagnosis of septic arthritis of the knee will be explained in thorough detail with the assistance of a Language Line Solutions certified translator if the patient is Spanish speaking. Informed consent for study inclusion will be obtained if the patient meets the above inclusion criteria.

**It must be emphasized that the patient's care is not to be delayed in order to obtain consent for study inclusion.** The study investigators include multiple orthopedic attending surgeons and residents. However, a situation may arise in which the study investigators are NOT available to explain the study and obtained informed consent. In this case, the patient's care is not to be delayed in order to ensure their inclusion in this study. They will be treated promptly to ensure appropriate patient care and will not be included in this study.

B.) If non-English speaking persons will be enrolled, state the informed consent process for enrolling the subjects, including who will conduct the consent interview, translated documents, etc. Exclusion of non-English speaking subjects from research requires ethical and scientific justification

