All non-english speaking persons will be offered study inclusion. Informed consent will be obtained utilizing a Spanish-translated consent form (after IRB approval). There are multiple Spanish speaking members of the research personnel and they will be obtaining Spanish consents. If one is not available, then a certified hospital interpreter will be utilized. If none are available, since UMC does not allow language line solutions to be used for research purposes, the patient will not be able to be consented and thus will not be included in the study.

C.) Indicate the population of subjects potentially able to participate in this study

All adult patients (>18 years) who have a clinically established diagnosis of septic arthritis in the emergency department based on the following will be considered for study inclusion and approached for offering participation in our study:

- Arthrocentesis with synovial WBC > 50,000 with left shift (85% PMNs)
- AcrySTALLINE (without gout crystals) elevated synovial WBC >25,000 with high clinical suspicion
- Willingness to participate in this research study

These patients are all indicated with formal operative irrigation and debridement of their knee, regardless of study inclusion. However, they will be excluded from study inclusion if they meet one of the following exclusion criteria:

- Recently treated septic arthritis (within past 3 months)
- If they have a prosthetic joint replacement to the affected knee
- Refusal to participate in the study

D.) Indicate the number needed

Our power analysis (beta =0.80, alpha = 0.05) shows the optimal sample size to be a minimum of 40 patients.

E.) List the inclusion/exclusion criteria

All adult patients (>18 years) who have a clinically established diagnosis of septic arthritis in the emergency department based on the following will be considered for study inclusion and approached for offering participation in our study:

- Arthrocentesis with synovial WBC > 50,000 with left shift (85% PMNs)
- AcrySTALLINE (without gout crystals) elevated synovial WBC >25,000 with

high clinical suspicion  
-Willingness to participate in this research study

These patients are all indicated with formal operative irrigation and debridement of their knee, regardless of study inclusion. However, they will be excluded from study inclusion if they meet one of the following exclusion criteria:

- Recently treated septic arthritis (within past 3 months)

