**Describe the following aspects of the study design:**

A.) Proposed study groups with number/group and treatments/group

Group 1: patients who undergo open surgical incision and drainage with debridement and irrigation (>20 patients)

Group 2: patients who undergo arthroscopic incision and drainage with debridement and irrigation (>20 patients)

B.) Describe the method used to determine the number of subjects needed

Power analysis utilized to determine a difference in the number of surgeries required to display apparent clinical resolution between open versus arthroscopic treatments (beta =0.80, alpha = 0.05) shows the optimal sample size to be a minimum of 40 patients.

C.) Describe how you determined that this number of subjects could be recruited

Power analysis. Additionally, [name] (CHRC/Research Manager MC EP Compliance) was contacted and was able to find a preliminary potential of 1,851 unique patient records from the year 2000 to the present who had septic arthritis. Even if only 20% of these patients met study inclusion/exclusion criteria, approximately 20 patients a year would be included. This would require 2-3 years of data collection in order to meet appropriate power analysis.

Anecdotally, the attending physicians serving as principal- and co-investigators believe they treat a minimum of 20 adult patients each per year with septic arthritis of the native knee.

D.) Method of randomization

Patients with medical record numbers ending in an EVEN number will undergo open surgical irrigation and debridement.

Patients with medical record numbers ending in an ODD number will undergo arthroscopic surgical irrigation and debridement.

E.) Schedule of events (i.e. control vs. treatment, number of visits)

All patients who present to the emergency department with a painful knee and clinical suspicion for septic arthritis undergo appropriate workup by the emergency department staff members. If there is a clinical suspicion for septic arthritis, the standard workup includes the following:

- assessment of vitals
- obtaining a history of the present illness
- performing an appropriate physical examination

If a provider determines that septic arthritis is part of their differential diagnosis, a basic serum laboratory workup is to be ordered. There will be a template created on the Cerner application to assist providers with a convenient, expedited manner of ordering these labs. These will include the following blood serum values:

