If the diagnosis of septic arthritis has been established, the diagnosis, pathogenesis and treatment options will be discussed with the patient. The current standard of care for the management of septic arthritis in the knee is operative incision and drainage of the joint with debridement and irrigation, obtaining intra operative cultures, then initiating antibiotic therapy. Non operative management would consist of antibiotic treatment alone. Should the patient decide to proceed with surgical intervention, an informed consent for surgery in the presence of a witness will be obtained, as per standard guidelines. At that time, the patient will be asked to participate in this study. If they agree, then the patient will be randomized into one of two groups:

1. Open surgical incision and drainage with debridement and irrigation
2. Arthroscopic incision and drainage with debridement and irrigation

An informed consent will be performed by one of the participating research investigators in the setting of a witness, as per standard guidelines. The surgical consent will be obtained at that time in a similar manner. If the patient declines to participate in this study, they will still be offered surgical intervention based on physician preference and their surgical ability.

All patients will be admitted after surgery for continued intravenous antibiotics and infectious disease consultation. Additionally, they will be followed for signs/symptoms that indicated a second surgery is required. The specific criteria for recurrence and failure of initial irrigation and debridement will be the following:

- persistent purulent discharge from a drain or incisional site
- increasing pain
- decreasing range of motion
- persistent fevers
- persistent elevation of serologic inflammatory markers

Patients showing steady clinical improvement after 72 hours post operatively will be discharged with continued antibiotic therapy targeted to bacteria if positive growth on cultures. If delayed growth occurs after patient discharge, they will be individually contacted for change to antibiotics if deemed appropriate, as is standard clinical practice. All study participants will have regularly 2-week and 6-week post-operative appointments where functional outcomes will be assessed in include physical exam, knee Lysholm scores and basic laboratory evaluation.

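### Allocation by the last digit of the medical record number is predictable before enrolment, so the trial is quasi-randomised and open to selection bias

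*Combined protocol and SAP*

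**What the plan says.** The study design section, item D (Method of randomization), consists of two rules: "Patients with medical record numbers ending in an EVEN number will undergo open surgical irrigation and debridement" and "Patients with medical record numbers ending in an ODD number will undergo arthroscopic surgical irrigation and debridement". Nothing else in the document describes a sequence, concealment or central assignment.

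Elsewhere the protocol describes something different. Item E (Schedule of events) places allocation after agreement to take part: "If they agree, then the patient will be randomized into one of two groups". The Significance section says: "This study would help solidify in a randomized control trial the most appropriate surgical approach to septic arthritis of the adult native knee". The Risks section also refers to patients as randomised.

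On the order of events, the informed consent section (Human Study Subjects, item A) has the treating resident contact an investigator once arthrocentesis confirms eligibility. Meanwhile "the orthopedic resident managing the patient's care will obtain consent for surgery and book the patient for the operating room". The same section accepts that "a situation may arise in which the study investigators are NOT available to explain the study"; such patients are treated promptly and left out of the study. Under Schedule of events, patients who decline have surgery according to the physician's preference and ability.

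**The concern.** Randomisation protects a comparison only if nobody who influences entry can foresee the next assignment. Here the assignment is a fixed property of the chart. The last digit may well be unrelated to prognosis among all patients who present. The bias comes from who is then enrolled: a clinician who thinks a patient is better served by one approach can see whether enrolment would deliver it, and can let the patient pass if not.

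The protocol supplies the motive. Its Significance section says that the choice of approach mostly follows the surgeon's own preference. At stake is the study's stated purpose, randomised evidence on the better approach. If severity differs between the arms because of selective entry, a difference in repeat surgery or length of stay cannot be attributed to the operation.

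**Working it through.** **1. Can the arm be known before entry is settled?** The document does not say when the record number is issued, so this step is an inference. Item E has serum and synovial tests ordered through templates in the electronic record before eligibility is confirmed, so the number very probably exists by then. These steps are still open at that point:

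- the second eligibility route, a synovial count above 25,000 without crystals, which also needs a judgement of high clinical suspicion;
- the resident's call to an investigator;
- whether an investigator is available (the investigators include orthopaedic attendings and residents);
- how the study is presented to the patient.

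No step after consent introduces chance, although item E says patients are randomised then.

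**2. Does anything offset this?** I found no blinding, no log of eligible patients by record-number parity and no statement that patients are analysed as assigned. Item A of the study design defines the groups by the operation patients undergo, and the list of key variables records the approach performed.

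**3. What could selective entry do?** The inputs are assumptions, not protocol figures: 40% of patients are severe, with 40% reoperated; the other 60% have 10% reoperated; the operation has no effect.

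- Open arm, no selection: 0.4 × 0.4 + 0.6 × 0.1 = 22.0%.
- Arthroscopy arm, a fraction *s* of severe patients not enrolled: severe share = 0.4(1 − s) / [0.4(1 − s) + 0.6]; reoperation = share × 0.4 + (1 − share) × 0.1.

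| s | Severe share | Arthroscopy | Open |
|---|---|---|---|
| 0.25 | 0.30/0.90 = 0.333 | 20.0% | 22.0% |
| 0.50 | 0.20/0.80 = 0.250 | 17.5% | 22.0% |
| 0.75 | 0.10/0.70 = 0.143 | 14.3% | 22.0% |

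**4. Effect on the false-positive rate.** Take 20 per arm, a two-sided t-test at 0.05 and no true effect. If selection shifts baseline prognosis by *b* standard deviations, the test statistic is noncentral t with 38 degrees of freedom and noncentrality b√10.

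| Assumed shift (SD) | False-positive rate |
|---|---|
| 0 | 5.0% |
| 0.1 | 6.1% |
| 0.2 | 9.5% |
| 0.3 | 15.2% |
| 0.5 | 33.8% |

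Under one specific mechanism (assumed: 30% severe, each 1 SD worse), leaving out 25%, 50% or 75% of severe cases from one arm gives 5.3%, 6.4% or 9.0%.

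**5. Arm sizes.** The plan gives a minimum of 40 patients and more than 20 per group. Treating parity as a fair coin with 40 patients:

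- P(20/20) = C(40,20)/2⁴⁰ = 12.5%.
- P(smaller arm ≤ 15) = 2 × P(X ≤ 15) = 15.4%, with X binomial(40, 0.5).
- For both arms to reach at least 20, about 48 patients give an 80% chance and 51 a 90% chance.

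The 40 itself cannot be reproduced, because the protocol states no effect size, standard deviation or event rate. The allocation point does not depend on it.

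**The case against.** The strongest reply is that the practical bias may be small. The protocol says every eligible adult will be approached, the main eligibility route is a laboratory threshold, and the unavailability clause exists to avoid delaying care. Theatre booking runs alongside the approach for study consent and is not itself a point where enrolment is chosen. In the half-skipped example the gap is 22.0 − 17.5 = 4.5 percentage points, or 0.9 of a patient in an arm of 20, and an uncorrected chi-square test would then reject 6.4% of the time, against about 5.0% with no shift. That example also uses a reoperation proportion, while the power analysis concerns the number of surgeries. The larger error rates arise only when a large imbalance is assumed.

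Most of this is fair as to size. The bias is possible, not demonstrated, and mild selection inflates error only modestly. But a rule to approach everyone does not conceal allocation, and without a screening log nobody could tell whether it had been followed. Adjustment cannot reliably remove selection on judgements that were never recorded.

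The arm-size argument is secondary. Nothing caps enrolment at 40, so recruitment could continue until both groups exceed 20. Even a 25/15 split lowers power only from 80.0% to 77.4% at the standardised difference that 20 per arm would detect (0.909, t-test). Imbalance in numbers is not bias.

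**Conclusion.** The concern holds and must be fixed. The method is deterministic allocation without concealment; the accurate label is quasi-randomised, and the protocol's own wording contradicts its method. This follows from the text and needs no calculation. The one inference is that the record number is visible before entry is decided, which the electronic ordering strongly supports.

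The size of any bias cannot be known from the documents. Under the assumed scenarios it runs from negligible (5.3% false positives) to serious (33.8%). As planned, the trial could not rule out the serious end, so it cannot support the claim of randomised evidence.

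**What to change.** Replace item D with a computer-generated 1:1 list in permuted blocks of varying size, prepared by the university statisticians whom the plan already names for checking the analysis. Reveal each assignment by a web tool, or by sequentially numbered, opaque, sealed envelopes, only after eligibility is recorded and study consent is signed. Record the assigned arm separately from the approach performed, and state that each patient is analysed in the assigned arm.

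Keep a log of all eligible patients, enrolled or not, with the reason for non-enrolment. If any patients have already been allocated by record number, report them as quasi-randomised, and tabulate eligible but unenrolled patients by parity where records allow.

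The cost is a protocol amendment, a list, a set of envelopes or a web form, and a short log. I would expect opening an assignment to take about a minute, so it need not conflict with the rule against delaying care. The sample-size figure is unchanged, no extra patients are needed, and blocking keeps the arms at or near equal size.

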**Background (literature review):** Please see abstract

**Specific Aims:** To determine if there is an overall difference in hospital length of stay and number of surgeries required to provide clinical resolution of septic arthritis of an adult native knee. Secondary outcomes will evaluate differences in knee range of motion, post operative pain levels, and overall patient satisfaction.

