Vitals, physical exam findings, and laboratory markers will be recorded in the clinical record and maintained within the patient's electronic medical record. The principal investigator will utilize the electronic medical record to record and maintain pertinent physical examination findings, laboratory markers, and treatments on a private, secured device. The only individuals who will be granted access to the device are co-investigators participating in this research study.

F.) List of Key Variables or Measurements to be done

- initial presenting arthrocentesis labs as well as serum lab values
- physical examination findings
- time from presentation to operative management
- type of surgical approach performed
- total operative time
- reason for necessity to return to operating room
- number of operative procedures required in order to establish clinical improvement**
- bacterial growth from arthrocentesis and operative cultures
- length of antibiotic course as deemed by infectious disease specialist
- hospital length of stay**
- Lysholm knee scores

G.) Assessment of subject safety and development of a data and safety monitoring plan

All data will be stored on a password locked external hard drive device. The password will only be provided to primary investigators of this study. The information recorded will be maintained on this device and stored in accordance with TTUHSC policies. The principal investigator will be responsible for version control and will ensure the study data are shared among team members in a secure fashion in accordance with TTUHSC/UMC guidelines (e.g., encrypted email, restricted-access share portal). The original email communications will be permanently deleted from the principle investigator's email inbox, outbox, and deleted folders.

Any unanticipated problems or other adverse events will be reported to the TTUHSC Human Protections Administrator. All unanticipated problems involving risk to subjects or others, adverse events, and all concerns related or possibly related to the study will be reported promptly to the TTUHSC Human Research Protections Office by providing

initial notification of the event as quickly as possible after the research team's knowledge of the event, but within five (5) business days.

H.) Create and attach your data collection form

This has been completed and filed with the IRB submission.

I.) Methods of data analysis (statistical analysis)

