Both [name] and [name] have served as statisticians in their previous roles as research assistants and have advanced training in statistical analysis. Regardless, the finalized data will be submitted to Texas Tech statisticians for validation and confirmation. Some of the anticipated statistical analysis tests are as follows:

Independent samples t-tests will be used to compare means of continuous and ordinal variables and p values less than 0.05 will be considered to represent a significant difference. For variables with Levene's Test for Equality of Variances greater than 0.05, equal variance is assumed. Pearson Chi-Square test p-values less than 0.05 will be considered to represent a significant difference in categorical variables. Fischer's exact test less will not be utilized as NCDB groups with  $n < 10$  are not to be included. ANOVA will be used to calculate significant differences in continuous and ordinal variables that have more than two categories. Paired samples t test and repeated measures ANOVA will be used to determine the progression of individual patients over time for continuous and ordinal variables respectively. Wilk's Lambda p-value less than 0.05 will be considered significant for repeated measures ANOVA and pairwise comparison will be used to determine the location of significance. Binary logistic regressions will be used to calculate odds ratios. Multivariate binary logistic regression may be attempted for all

significant variables. Receiver Operator Characteristic (ROC) may be calculated for significant continuous variables to determine the existence of a threshold that maximized sensitivity and specificity. All analysis will likely be performed by [name] on SPSS version 25 (IBM Corp. Released 2018. IBM SPSS Statistics for Macintosh, Version 25.0. Armonk, NY: IBM Corp).

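### The Levene pre-test makes the t-test's error rate depend on how the arms happen to split; using Welch's test throughout is a minor, cheap improvement

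*Combined protocol and SAP*

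**What the plan says.** Study-design item I sets the between-arm method: "Independent samples t-tests will be used to compare means of continuous and ordinal variables", with significance at p below 0.05. It then adds a variance rule: "For variables with Levene's Test for Equality of Variances greater than 0.05, equal variance is assumed". What happens when Levene's test is significant is not written out; the unequal-variance t-test is implied. The list is introduced tentatively ("Some of the anticipated statistical analysis tests are as follows"), but no other variance rule appears.

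The rule reaches outcomes that matter. The Specific Aims are "To determine if there is an overall difference in hospital length of stay and number of surgeries required", and the list of key variables (item F) marks "hospital length of stay" as a main measure and also includes "total operative time".

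Arm sizes are not fixed. Item D allocates by the last digit of the medical record number: "Patients with medical record numbers ending in an EVEN number will undergo open surgical irrigation and debridement", and odd numbers go to arthroscopy. No blocking is described. Item A gives each arm a floor rather than a size: "Group 1: patients who undergo open surgical incision and drainage with debridement and irrigation (>20 patients", with the same figure for the arthroscopic group. Item B gives a minimum total of 40.

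**The concern.** At about 20 per arm, a non-significant Levene test is weak evidence that the variances are equal, so the pooled t-test will often be kept when the SDs differ. With equal arms that does no harm. With unequal arms the pooled standard error is wrong in a direction set by which arm is more variable. It is too small, giving too many false positives and intervals that are too narrow, when the smaller arm has the larger SD. It is too large in the reverse case. The p-value for the one split that the trial obtains then does not carry its stated error rate, and a data-driven choice of test has been added that is better settled before the data are seen.

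**Working it through.** **Inputs.** From the documents: N at least 40, more than 20 per arm, alpha 0.05, the Levene threshold of 0.05, parity allocation. Assumed: two-sided tests, mean-centred Levene, Welch as the unwritten branch, a 50:50 chance of an even number, SD ratios of 1.5 and 1.8.

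**The plan's own figure.** The minimum of 40 cannot be reproduced, because no effect size or SD is given. Reading the stated beta of 0.80 as power and working back from 20 per arm: d = (1.96 + 0.84) × √(2/20) = 0.89, or 0.91 with the t distribution. A true difference of 0.9 SD is used for the power cost below.

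**1. How often Levene misses.** At 20/20 with normal data, the pooled test is kept in 65% of trials at SD ratio 1.5 and 38% at ratio 1.8. With a median-centred Levene test the first figure is about 70%.

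**2. How unequal the arms can be.** With N = 40 and X ~ Binomial(40, 0.5):
- P(20/20) = C(40,20)/2^40 = 12.5%
- P(24/16 or worse) = 2·P(X ≤ 16) = 26.8%
- P(26/14 or worse) = 2·P(X ≤ 14) = 8.1%

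If enrolment instead runs until both arms reach 21, the larger arm's median size is 25, and it is at least 1.5 times the smaller one 12.7% of the time.

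**3. Why the split matters.** The pooled variance of the difference has expectation [(n1−1)s1² + (n2−1)s2²]/(n1+n2−2) × (1/n1 + 1/n2). The true variance is s1²/n1 + s2²/n2. Take 24/16 with SD 1.5 in the smaller arm and 1 in the larger:
- Pooled: (23×1 + 15×2.25)/38 × (1/24 + 1/16) = 1.493 × 0.1042 = 0.1556
- True: 1/24 + 2.25/16 = 0.1823
- Ratio of standard errors: √(0.1556/0.1823) = 0.92

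With the larger arm more variable, the same calculation gives √(0.1830/0.1563) = 1.08. At 20/20 both variances equal 3.25/20 = 0.1625, so the ratio is exactly 1.

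**4. Error rate of the rule.** Simulated, normal data, equal means, 100,000 trials per setting; the ranges cover SD ratios 1.5 and 1.8.

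| Split | Rule, smaller arm more variable | Rule, larger arm more variable | Welch |
|---|---|---|---|
| 20/20 | 4.9-5.0% | same | 4.9-5.0% |
| 25/21 | 5.3-5.4% | 4.6-4.9% | 4.9-5.1% |
| 32/21 | 5.7-6.0% | 4.4-4.6% | 5.0-5.1% |
| 24/16 | 6.0% | 4.2-4.4% | 4.9-5.1% |
| 26/14 | 6.5-6.6% | 3.8-4.1% | 4.9-5.0% |

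Further runs at 26/14 and ratio 1.5 gave 6.7% and 6.8%. Averaged over all splits of 40, the rule runs at 5.0-5.1% and Welch at 4.9-5.0%. For normal data, these are also the miss rates of the 95% CI when a real difference exists.

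**5. Skewed data.** Stays were modelled as a 3-day floor plus a skewed excess, with equal means, 24/16 and 26/14, and the smaller arm more variable. Under mild skew Welch's error is 0.1-1.0 point lower than the rule's. Under strong skew it is between 0.8 point worse and 0.3 point better, and both run at about 6-8%.

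**6. Power cost of Welch.** Equal SDs, difference 0.9 SD:
- 20/20: 79.17% against 79.09% (0.1 point)
- 22/18: 78.69% against 78.51% (0.2)
- 24/16: 77.58% against 77.12% (0.5)
- 26/14: 75.21% against 74.30% (0.9)

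With skewed stays, the excess doubled and a 24/16 split, Welch loses 0.7-3.3 points if the longer-stay arm is the smaller one and gains 0.6-4.4 if it is the larger.

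**The case against.** **The 65% miss rate is not a harm in itself.** A reader might infer that the wrong test is used, and the result is wrong, about two times in three. The documents do not support that: the figure is for 20/20, where the rule and Welch agree to within 0.1 point. This stands.

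**The trial's overall error rate is not inflated.** Averaged over the splits that parity allocation can give, the rule holds its level. Only the error rate for an unequal split obtained is affected. This stands too, although the trial will be read from one split.

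**The larger figures use arms below target.** 24/16 and 26/14 fall short of more than 20 per group. At 25/21 the rule is within about half a point of nominal. This is fair. The stated minimum total of 40 still leaves those splits possible, and 32/21 satisfies the target with 5.7-6.0%.

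**False positives need a special null**, in which the approaches change the SD but not the mean. If the arms have identical distributions, the rule gives 4.9-5.2% with normal data and 4.4-5.0% with skewed data. That is right. Interval coverage under a real difference is the more relevant consequence, and the plan does not at present ask for an interval.

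**Length of stay may be skewed**, with discharge considered only after 72 hours. With the excess doubled at 25/21, the interval miss rate is 6.0-6.8% for the rule and 5.8-6.5% for Welch if the smaller arm is more variable. In the reverse case it is 5.2-5.7% and 5.4-5.8%. So it would be wrong to infer that Welch rescues a strongly skewed length of stay, or that a benefit has been shown for the number of surgeries, the outcome on which the sample size rests.

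**The tests are only anticipated**, and institutional statisticians will validate the analysis. That leaves room to correct the rule but does not replace it.

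**Conclusion.** The point holds as a minor improvement, not as an error that threatens the trial's conclusions. The Levene rule makes the error rate for the split obtained depend on which arm is more variable. The departure from 5% is about half a point or less at 25/21 and roughly 1 to 1.6 points at 24/16 to 26/14 when the smaller arm is more variable; in the reverse case the test is conservative by 0.6 to 1.2 points. It vanishes at 20/20 and cancels on average.

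These sizes rest on near-normal data and on assumed SD ratios of 1.5-1.8, for which the documents give no evidence either way. Whether a comparison of means suits a skewed or count outcome is a separate question, not settled here.

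**What to change.** Delete the Levene sentence from study-design item I and state that, wherever two means are compared, Welch's t-test will be used and the mean difference reported with its 95% CI.

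The cost is one sentence, with no extra patients or data. The planned software must already provide the unequal-variance test for the implied branch of the present rule. The change is not wholly free: the power figures above show a small loss with equal SDs, and a shift in either direction with skewed stays in an unequal split.

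Optionally, a log-scale Welch analysis of length of stay (ratio of geometric means with 95% CI) could be pre-specified as a sensitivity analysis. No gain in power is claimed for it, because that would depend on a distribution and an effect size that the documents do not give.
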